**Which Committee will review this protocol?**

The Clinical Research Committee - (CRC)

# **Treatment of Relapsed or Refractory Acute Lymphoblastic Leukemia (ALL) with CMC-544 (Inotuzumab Ozogamycin), with or without Later Addition of Rituximab**

## **1.0 Objectives**

- To evaluate the efficacy of treatment with CMC-544 with or without later rituximab in patients with relapsed or refractory ALL.
- To evaluate the side effects of the treatment.

## **2.0 Background**

### **2.1 Acute Lymphoblastic Leukemia (ALL)**

Adult ALL encompasses a heterogeneous group of lymphoid malignancies. Prognosis is related to age, karyotype, molecular profile, immunophenotype, and other disease features. Prognosis for pediatric ALL has improved significantly over the last several decades to current long-term survival rates of greater than 80% (1). However, long-term survival in adults is currently only 35% to 45% (2,3). The predominant reason for failure is disease recurrence.

The hyper-CVAD regimen (hyperfractionated cyclophosphamide, vincristine, doxorubicin, and dexamethasone alternating with high dose methotrexate and ara-C) (4,5), developed at M. D. Anderson, demonstrated significant activity, producing a complete remission (CR) rate of 90% and a cure rate of 40%-50%.

Current outcomes of salvage chemotherapy for ALL are poor, with complete response rates of 20% to 30% depending on prior therapy and duration of first remission. Median disease-free survival ranges from 2 to 7.5 months. Long-term survival after ALL salvage therapy is rare. Less than 10% of patients are eligible for allogeneic stem cell transplant. Among them the cure rate is 20% or less. No standard of care has been defined, so that salvage therapy options are generally limited to investigational agents once patients fail standard chemotherapy regimens(6,7). Not many treatments are available for ALL salvage.

New agents or regimens are needed to improve outcome in ALL. ALL blasts express several surface markers including CD19, CD20, and CD22. CD22 is expressed on the surface of ALL blasts in more than 90% of patients. Several new monoclonal antibodies have been developed that target these surface markers. Monoclonal antibodies with proven efficacy against ALL could potentially, when used in combination with chemotherapy, significantly improve ALL prognosis. For example, rituximab has minimal single agent activity in ALL but, when added to hyper-CVAD, has improved significantly the outcome in Burkitt's ALL and in CD20-positive pre-B ALL.

## **2.2 The Treatment -- CMC-544 (Inotuzumab Ozogamicin) and Rituximab**

CMC-544 (inotuzumab ozogamicin) is a CD22-targeted cytotoxic agent composed of a humanized IgG4 anti-CD22 antibody covalently linked to N-acetyl-g-calicheamicin dimethyl hydrazide (CalichDMH) via the acid-labile 4-(4V-acetylphenoxy) butanoic acid linker (8-10). CD22 is a B-lymphoid lineage-specific differentiation antigen expressed

on both normal and malignant B cells. CMC-544 binds CD22 with subnanomolar affinity, and, upon binding, is rapidly internalized delivering the conjugated CalichDMH inside the cells. This preferential intracellular delivery of CalichDMH causes DNA damage resulting in B-cellular apoptosis. CalichDMH is a derivative of g-calicheamicin, a natural product produced by *Micromonospora echinospora* and is significantly more potent than cytotoxic chemotherapeutic agents used in cancer therapy. It binds in the minor groove of DNA and causes double strand DNA breaks in a relatively sequence-specific and thioldependent manner leading to apoptotic response in cells (11-13). CMC-544 exerts potent and CD22-selective growth inhibitory activity against CD22+ B-cell lymphoma (BCL) cell lines in vitro and causes regression of developing (minimal disease), small established (palpable disease), and large BCL xenografts, with a high therapeutic index (9). In addition, CMC-544 had in vitro high activity against CD22 positive ALL cell lines (14). In the absence of the conjugated CalichDMH, G5/44, the targeting monoclonal antibody (mAb) in CMC-544 is ineffective in vivo as an antitumor agent in various preclinical models (8). Thus, CMC-544 is regarded as an antibody-targeted chemotherapy agent rather than an immunotherapeutic agent like rituximab. Largely due to its tumor-targeted, drug-delivery capability, CMC-544 is likely to have a better therapeutic index than that of conventional chemotherapeutic agents. Based on its potent antitumor activity in preclinical models, CMC-544 is currently being evaluated in patients with B-cell non-Hodgkin lymphoma (B-NHL). Early results show encouraging activity with response rates of 40% to 75% in patients with refractory relapsed BNHL(15). CD22 is expressed on leukemic blasts in more than 90% of adults with ALL. Thus, CMC-544 may be also an effective treatment for ALL.

Rituximab is a chimeric human IgG1 antibody targeted to another B-lymphoid lineage-specific molecule, CD20. It represents a major therapeutic advance in B-NHL therapy. Rituximab mediates its antitumor activity by multiple mechanisms that include complement-dependent cytotoxicity (CDC), antibody-dependent cellular cytotoxicity (ADCC), and direct induction of apoptosis in BCL (16-17). The activity of single agent rituximab is modest in BNHL, chronic lymphocytic leukemia, and ALL. However when combined with chemotherapy it has improved outcome significantly in all 3 entities (18-21).

### **2.3 Rationale for the Study Design**

Due to its clinical safety, rituximab is widely used in combination with various cytotoxic agents. Treatments using combinations of rituximab with cytoreductive combination chemotherapy, like CHOP (a combination of cyclophosphamide, doxorubicin, vincristine, and prednisone), hyper-CVAD, or fludarabine-cyclophosphamide are highly active. However, such combinations of chemoimmunotherapy also suffer from various systemic toxicities associated with the non-targeted nature of chemotherapy. Thus, studies of targeted therapy combinations like CMC-544 (target CD22) and rituximab (targets CD20) in pre-B ALL would be highly attractive, because of the potential of high efficacy and low toxicity. This is the purpose of this study. If successful, this combined targeted therapy may become a new standard of care for patients with refractory relapsed ALL. It may also be brought into frontline therapy of minimal residual disease to increase the

cure of patients with newly diagnosed pre-B ALL. Thus the study has major potential therapeutic implications for improving adult ALL prognosis.

The phase I-II studies of CMC-544 determined the phase II dose to be 1.8 mg/m^2 once every 3-4 weeks. The DLT was myelosuppression. Other side effects were gastrointestinal and hepatic. Only 1 case of veno occlusive disease was noted among 176 patients treated(14). Phase II studies combining rituximab 375 mg/m^2 on Day 1 and CMC-544 1.8 mg/m^2 on Day 2 were safe and effective in lymphomas(15).

#### **2.4      Update of October 6, 2010**

At present, a total of 21 patients with refractory relapse ALL have been treated. Fifteen of them were in second salvage or worse; eight of them have translocation 4;11 or Philadelphia positive ALL. Overall, 12 of 21 patients have achieved either CR (n=5) or Cri (n=7), for an overall response rate of 57%. This is even better than what is expected using standard combination intensive chemotherapy in first salvage, with which the CR rate would be expected to be about 30%. Toxicity has been minimal. There were two episodes of tumor lysis responding to standard measures. Fever on Day 2 post therapy is common. Transient grade 1-3 elevations of liver enzymes have been observed, which are expected and self-limited. Two patients died within four weeks, one of them with progressive disease. Overall the treatment appears to be extremely effective with minimal toxicity. This has allowed so far at least 4 patients to undergo allogeneic stem cell transplant. Based on the findings we propose to 1) allow treatment of patients in first salvage regardless of the duration of first CR, and 2) increase the total number of

patients to 60 to allow more accurate assessment of the overall response rate and define more precisely predictive factors for response to therapy.

## **2.5 Update of January 7, 2011**

At the present update, 38 patients have been treated. Of 32 evaluable patients, 8 achieved CR and 10 achieved CRI or CRp for an overall response rate of 18/32 =56%. Toxicities were reasonable and included Grade 1-2 elevations of liver function tests which were transient. Two patients had Grade 3 liver function abnormalities; the attribution to the drug was questionable.

From preclinical studies, it is thought that lower dose more frequent exposure schedules to inotuzumab may offer better anti-ALL efficacy. Following discussions in the Leukemia group and with Pfizer investigators, it was decided to study a different schedule of inotuzumab given weekly times 3. The total dose per course is the same, 1.8 mg/m^2. The treatment will be with inotuzumab 0.8 mg/m^2 on Day 1, 0.5 mg/m^2 on Day 8, and 0.5 mg/m^2 on Day 15. Courses are given every 3 weeks. When rituximab is required, it will be given weekly with inotuzumab. A total of 20 patients will be treated to gain experience with efficacy and toxicity. Early stopping rules will be implemented for an overall response rate < 40%.

## **2.6 Update of December 2, 2011**

This study has completed accrual of 20 patients on the weekly schedule. The early analysis shows encouraging results with trends for similar or better efficacy and less

toxicity. Among the first 15 evaluable patients, 2 achieved CR (12%), 5 achieved CRp (31%) and 1 achieved CRi (6%). Thus, 8 of 15 evaluable patients (53%) achieved marrow CR. Five of the 7 evaluable responders (71%) achieved MRD negativity. Three patients underwent allogeneic SCT; no VODs were noted. Transient liver enzyme elevations grade 1-2 were noted in 5 of 20 (25%), severe in 2.

In discussions with Pfizer, we emphasized the importance of these findings but the limited number of patients makes definite conclusions difficult. It was agreed to increase the number of treated patients on the weekly schedule by another 20, for a total of 40 patients, to assess more precisely the response and toxicity profile compared with the 49 patients treated with the single dose every 3-4 weeks.

### **3.0 Background Drug Information**

#### **3.1 Inotuzumab Ozogamicin Nonclinical Data**

Inotuzumab ozogamicin is an antibody-targeted intravenous (IV) chemotherapy agent composed of an antibody, targeting CD22 antigen, which is linked to calicheamicin, a potent cytotoxic antitumor antibiotic. The targeting agent in inotuzumab ozogamicin is a humanized IgG4 antibody, G544 that specifically recognizes human CD22. Being an IgG4 isotype antibody, G544 is not expected to mediate effector functions such as complement-dependent cytotoxicity or antibody-dependent cellular cytotoxicity. CD22 is expressed on both normal and malignant cells of the mature B-lymphocyte lineage. Nonmalignant, mature lymphocytes express CD22; however, lymphocyte precursor

cells and memory B cells do not express CD22. Thus, the impact of treatment with inotuzumab ozogamicin on long-term immune function is expected to be minimal.

The concept of antibody-targeted chemotherapy has been successfully translated into a clinically validated therapeutic agent, gemtuzumab ozogamicin (Mylotarg). N-acetyl calicheamicin dimethyl hydrazide (N-acetyl calicheamicin DMH), the cytotoxic entity in both inotuzumab ozogamicin and gemtuzumab ozogamicin, is a derivative of calicheamicin methyl trisulfide.

N-acetyl calicheamicin DMH is at least 100- to 1000-fold more potent than current cytotoxic therapeutics, such as doxorubicin. Its high potency makes N-acetyl calicheamicin DMH an ideal candidate for antibody-targeted chemotherapy.

Inotuzumab ozogamicin is expected to have greater efficacy than unlabeled monoclonal antibodies and to have efficacy at least comparable to the leading chemotherapeutic or radio-immunoconjugate based therapies. Because of its targeted nature, it is expected to have a reduced incidence of side effects compared with conventional cytotoxic chemotherapy or radioimmunotherapy. This may confer important advantages in tolerability and reduced need for supportive care for subjects treated with inotuzumab ozogamicin as a single agent and offers the potential to intensify combination regimens without substantial additional toxicity.

CD22 was chosen as a target for conjugate delivery for a number of reasons. CD22 is expressed on the malignant cells of the majority of B-lymphocyte malignancies. It is not expressed on hematopoietic stem cells or any other nonlymphoid hematopoietic or nonhematopoietic cells.

Moreover, based on in vitro testing of human NHL cell lines, CD22 is one of the better internalizing molecules among several B- lymphoid lineage-specific surface antigens and is not shed into the extracellular environment. The normal function of CD22 is to regulate signal transduction of the surface immunoglobulin receptors on B cells.

Inotuzumab ozogamicin exhibits a potent dose-dependent cytotoxicity in vitro and in vivo animal tumor models. Unconjugated G544 does not fix complement, does not mediate antibody-dependent-cellular cytotoxicity, and has no antitumor activity. In addition, inotuzumab ozogamicin was effective against human B-cell lymphomas in nonclinical murine models in which rituximab, a chimeric anti-CD20 monoclonal antibody, had failed as a therapeutic agent.

This important nonclinical therapeutic advantage conferred by inotuzumab ozogamicin strongly supports its targeted clinical application in NHL. Nonclinical data also indicate a synergistic effect between inotuzumab ozogamicin and rituximab, as the combination of inotuzumab ozogamicin plus rituximab was: (a) more efficacious against established subcutaneous Ramos B lymphoma xenografts in nude mice, and (b) increased long term survival of severe immunodeficient mice with disseminated Ramos B lymphoma

than either agent alone (22). See the most recent version of the investigator's brochure for all nonclinical data that potentially have a clinical significance and from clinical studies that are relevant to this study (23). Also refer to the most recent version of the investigator's brochure for a summary of the known and potential risks and benefits, if any, to human subjects.

### **3.2 Inotuzumab Ozogamicin Clinical Data**

The first in human trial (3129K1-100-WW [100-WW]) of inotuzumab ozogamicin was an open-label, dose-escalating, single-agent study in 79 subjects with CD22-positive B-cell NHL(23).

The study defined the maximum-tolerated dose and showed a safety profile (and preliminary efficacy data) that supported advancement of inotuzumab ozogamicin's clinical development(8,9,22).

This continued clinical development included initiation of 4 additional trials (2 global and 2 in Japan) involving the use of inotuzumab ozogamicin as either a single agent or in combination with rituximab for treatment of CD22-positive B-cell NHL. The combination strategy was evaluated since B-NHL cells consistently express both CD20 and CD22; thus, it is reasonable to combine rituximab and inotuzumab ozogamicin (anti-CD20 and CD22 targeting antibodies, respectively) in an attempt to enhance the therapeutic advantage of either agent. Nonclinical data supported this reasoning (see Inotuzumab Ozogamicin Nonclinical Data section).

The following safety and efficacy discussions focus on 2 of the 5 studies currently comprising the clinical development of inotuzumab ozogamicin (studies 100-WW and 3129K3-101-WW [101-WW]) since these are global trials that include patients with DLBCL. Furthermore, because response data are available by NHL class, efficacy discussions for studies 100-WW and 101-WW will focus on patients with diffuse large B-cell lymphoma (DLBCL).

### **3.2.1 Study 100-WW: Safety and Efficacy of Single-agent Inotuzumab**

**Ozogamicin.** Study 100-WW was a phase 1, open-label, dose-escalation study of the safety, tolerability, and pharmacokinetics (PK) of inotuzumab ozogamicin administered as a single-agent to 79 subjects with CD22-positive B-cell NHL. Dose escalation was based on safety evaluations through days 21 to 28 after the first dose of inotuzumab ozogamicin. The maximum tolerated dose (MTD) was determined to be 1.8 mg/m^2 given every 28 days. Of the 49 subjects in the MTD cohort, 26 subjects had DLBCL. All 79 subjects in the study had received prior chemotherapy, immunotherapy, or hormonal therapy per the inclusion criteria defined in the protocol, and most subjects (60.8%) had received at least 4 prior treatment regimens. Subjects ranged in age from 26 to 82 years (median, 60 years).

The most common treatment emergent adverse events (TEAEs, incidence  $\geq$  20% of subjects) were hematologic (thrombocytopenia [84.8%], neutropenia [43.0%], anemia [22.8%], and leukopenia [21.5%]); gastrointestinal (nausea [51.9%], anorexia [31.6%],

constipation [24.1%], and vomiting and diarrhea [21.5% each]); metabolic (aspartate aminotransferase [AST] increased [39.2%], alkaline phosphatase increased [26.6%], alanine aminotransferase [ALT] increased [21.5%], and bilirubinemia [20.3%]); respiratory (cough increased [21.5%]); asthenia (65.8%); fever (39.2%); abdominal pain (35.4%); and headache (21.5%). The most common grade 3/4 TEAEs (incidence  $\geq$  5% of subjects) were predominantly hematologic or metabolic: thrombocytopenia (59.5%), neutropenia (25.3%), leukopenia (13.9%), lymphopenia (11.4%), and anemia and hypokalemia (6.3% each). Others were: asthenia (10.1%) and gamma glutamyl transpeptidase (GGT) increased (6.3%) increased blood fibrinogen, blood lactate dehydrogenase, and venoocclusive disease among adverse reactions or as adverse reactions leading to the discontinuation of the drug. Dose-limiting toxicities were all hematologic events: 3 cases of grade 4 thrombocytopenia, 1 event of bleeding (injury-related) that required a platelet transfusion because of concurrent thrombocytopenia, and 1 event of grade 4 neutropenia. Fifteen (15) subjects with DLBCL in the expanded MTD cohort were evaluable for tumor response (**24**) (received  $\geq$  2 doses of inotuzumab ozogamicin and had tumor assessments at both baseline and postbaseline visits). These subjects had a best overall response rate (ORR) of 47.0% (2 CR and 5 PR), a median progression-free-survival (PFS) of 105 days (95% confidence interval [CI], 55 to 343), and a median overall survival (OS) of 273 days (95% CI, 168 to 518).

**3.2.2 Study 101-WW: Safety and Efficacy of Inotuzumab Ozogamicin in Combination with Rituximab.** Study 101-WW is an ongoing phase 1/2, open-label, dose-escalation study of the safety, tolerability, and PK of inotuzumab ozogamicin in

combination with rituximab in patients with relapsed DLBCL or follicular NHL. Subjects for whom curative therapies were available (ie, high-dose (HD) chemo and a stem cell transplant [SCT] for DLBCL) were not eligible for the study. Subjects who had relapsed after obtaining a response (progressed > 6 months after start of prior therapy) to first or second line rituximab-containing therapies were eligible for participation. For this ongoing study, the following results reflect data available as of September 23, 2008 (a third cohort recently opened to enroll 30 subjects with DLBCL that is refractory to treatment with rituximab in combination with chemotherapy [ie, progressed ≤ 6 months of start of prior therapy]; no safety or efficacy data is currently available for this new cohort). In total, 74 subjects have received study drug, including 66 subjects (27 with DLBCL) treated at the MTD (375 mg/m^2 rituximab on day 1, and 1.8 mg/m^2 inotuzumab ozogamicin on day 2). Subjects ranged in age from 29 to 85 years (median, 65.5 years) and most (54%) had received 2 prior lines of therapy.

The observed TEAEs are those characteristic of rituximab and inotuzumab ozogamicin when administered as single agents. The most common TEAEs (incidence ≥ 20% of subjects) were hematologic (thrombocytopenia [40.5%], neutropenia [23.0%]); gastrointestinal (nausea [51.4%], constipation [21.6%], and vomiting [24.3%]); metabolic (AST increased [33.8%]); fatigue (43.2%); infections (40.5%); pyrexia (29.7%); headache (20.3%); and vascular disorders (20.3%). The most common grade 3/4 TEAEs (incidence ≥ 5% of subjects) were predominantly hematologic (thrombocytopenia [21.6%], neutropenia [17.6%], and lymphopenia [5.4%]). Others

were: gastrointestinal (5.4%) or general (8.1%) disorders, infections (8.1%), and abnormal laboratory results (10.8%).

A best overall response rate (ORR) of 79% (80% CI, 64.8% to 89.5%) has been achieved for 24 DLBCL subjects treated at the MTD. Informal analyses of current data indicate that the response rate is unaffected by both the number and duration of response to prior therapies, as well as IPI score and age: best ORRs were 80% (N =15) and 78% (N = 9) for subjects with 1 and 2 prior line of therapy, respectively; 75% (N = 8) and 81% (N = 16) for subjects with prior response durations of < 12 and  $\geq$  12 months, respectively; 72% (N = 18) and 100% (N = 6) for subjects with IPI scores > 1 and < 2, respectively; and 87.5% (N = 8) and 75% (N = 16) for subjects < 60 and > 60 years of age, respectively. At the time of evaluation (September 23, 2008), these 24 subjects have a 6-month PFS rate of 65% (80% CI, 48% to 78%).

## **4.0 Patient Eligibility**

### **4.1 Inclusion Criteria:**

1. Previously treated ALL (including Burkitt's lymphoma and lymphoblastic lymphoma) in relapse or primary refractory. Patients in first relapse will be eligible regardless of the first remission duration. At least 10 patients in Salvage 1-2 will be treated to assess anti-ALL response more precisely.
2. Age 16 years or older. Pediatric patients (<16 years old) will be allowed into the study after safety is established, that is at least 10 adult patients having received 1 or more cycles each.

3. Zubrod performance status 0-3.
4. Adequate liver function (bilirubin  $\leq$  1.5 mg/dL and SGPT or SGOT  $\leq$  3 x upper limit of normal [ULN], unless considered due to tumor), and renal function (creatinine  $\leq$  2 mg/dL). Even if organ function abnormalities are considered due to tumor, the upper limit for bilirubin is  $\leq$  2.0 mg/dL and creatinine  $\leq$  3 mg/dL.
5. Male and female patients who are of childbearing potential agree to use an effective barrier method of birth control (e.g., latex condom, diaphragm, cervical cap, etc.) to avoid pregnancy. Female patients need a negative serum or urine pregnancy test within 14 days of study start (applies only if patient is of childbearing potential. Non-childbearing is defined as  $\geq$  1 year postmenopausal or surgically sterilized).

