#### **4.2 Exclusion Criteria:**

1. Patient with active heart disease (NYHA class  $\geq$  3 as assessed by history and physical examination).
2. Patients with a cardiac ejection fraction (as measured by either MUGA or echocardiogram)  $<$  45% are excluded.
3. Patients who receive other chemotherapy. Patients must have been off previous therapy for  $\geq$  2 weeks and must have recovered from acute toxicity (to grade 1 or less) of all previous therapy prior to enrollment (consent signing). (Concurrent therapy for central nervous system [CNS] prophylaxis or treatment for CNS relapse is permitted). Treatment may start earlier if

necessitated by the patient's medical condition (e.g. rapidly progressive disease) following discussion with the Principal Investigator.

4. Prior allogeneic stem cell transplant in previous 4 months.
5. Peripheral lymphoblasts  $> 50 \times 10^9/L$ .
6. Pregnant and breast-feeding patients are excluded.
7. Patients with known hepatitis B are excluded.

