Infusion 1 of rituximab will be over 6-8 hours following infusion rate increases as per hospital standards. Infusions 2-6 of rituximab may be run at faster rates of 2-6 hours as indicated by side effects and per hospital standards.

**5.2.4** Patients achieving response, defined as CR or CRi, or partial remission (PR) may continue therapy for up to 8 cycles (about 8-12 months of therapy). Patients with progression at any time or without objective response after 3 cycles will be taken off study.

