## **8.0 Criteria for Response**

**8.1 Complete remission (CR):** Disappearance of all clinical and/or radiologic evidence of disease. Neutrophil count  $\geq 1.0 \times 10^9 /L$ , platelet count  $\geq 100 \times 10^9 /L$ , and normal marrow differential ( $\leq 5\%$  blasts).

**8.2 Complete remission without recovery of counts (CRI):** Peripheral blood and marrow results as for CR, but with incomplete recover of counts (platelets  $< 100 \times 10^9 /L$ ; neutrophils  $< 1 \times 10^9 /L$ ).

**8.3 Partial remission (PR):** Peripheral blood count recovery as for CR, but with decrease in marrow blasts of  $\geq 50\%$  and not more than 25% abnormal cells in the marrow.

**8.4 Other:** All other responses will be considered as failures.

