## **9.0 Criteria for Removal from the Study**

The Investigator may remove patients from the study for any of the following reasons:

**9.1 Progressive disease.** This is defined as a doubling of the peripheral blasts and an absolute increase of  $> 5 \times 10^9/L$ .

**9.2** Unacceptable adverse events/toxicities (any  $>/=$  grade 3 non-hematologic toxicity that does not at least resolve to < grade 2 or baseline).

**9.3** Investigator thinks a change of therapy would be in the best interest of the patient.

**9.4** If the patient has intercurrent, non-leukemia-related illness that would, in the judgment of the Investigator, affect assessments of clinical status to a significant degree and require discontinuation of protocol therapy.

**9.5** Patient request.

**9.6** Patient is non-compliant with protocol requirements.

The Principal Investigator has the right to terminate this study at any time. Reasons for terminating the study may include, but are not limited to:

**9.7** If the incidence or severity of adverse events indicates a potential health hazard to patients.

**9.8** If the patient enrollment is unsatisfactory.

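### CRi and PR have no extramedullary condition, and no scheduled test supports the radiologic part of CR, although Section 4.1 admits lymphoma and sets no marrow blast minimum

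*Combined protocol and SAP*

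**What the plan says.** **Who is eligible.** Section 4.1, item 1 takes "Previously treated ALL (including Burkitt's lymphoma and lymphoblastic lymphoma) in relapse or primary refractory". Neither 4.1 nor 4.2 sets a minimum for marrow blasts, platelets or neutrophils. Section 4.2, item 3 adds that "Concurrent therapy for central nervous system [CNS] prophylaxis or treatment for CNS relapse is permitted", so disease outside the marrow is foreseen at entry.

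**How response is scored.** Section 11.0 makes CR, CRi or PR the primary efficacy endpoint, and the futility rule there counts the same three categories. Section 8.0 defines them:
- CR (8.1): "Disappearance of all clinical and/or radiologic evidence of disease", plus recovered counts and marrow blasts of 5% or less.
- CRi (8.2): "Peripheral blood and marrow results as for CR, but with incomplete recover of counts".
- PR (8.3): "Peripheral blood count recovery as for CR, but with decrease in marrow blasts of" at least 50%, with no more than 25% abnormal marrow cells.
- Anything else (8.4) is a failure.

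**What is measured.** Sections 6.0 and 7.0 schedule physical examination, blood tests and marrow. The only radiology mentioned is a work-up for abdominal pain when needed. No disease imaging or CSF examination is scheduled.

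**Progression.** Section 9.1 rests on circulating blasts alone: "This is defined as a doubling of the peripheral blasts and an absolute increase of" more than 5 x 10^9/L.

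**The concern.** Eligibility reaches patients whose disease lies wholly or partly outside the marrow, but two of the three response categories look only at blood and marrow. For a patient whose marrow was never involved, the marrow condition is met before the first dose and says nothing about the drug. The same wording gives no credit for a real partial response in a node or mediastinal mass.

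Response feeds the primary estimate, the stopping rules in Sections 11.0 and 11.2, the descriptive comparison of the two schedules (Section 2.6), and any reading against the 20% to 30% complete response rate that Section 2.1 gives for ALL salvage chemotherapy. Response status also governs the treatment steps in Sections 5.2 and 5.3, so a wrong classification reaches beyond the analysis.

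**Working it through.** **1. The plan's own figures.** The futility rule in Section 11.0 stops if Pr(theta > 0.20 | data) < 0.10 with a beta(1,1) prior, so the posterior after x responses in n patients is beta(1+x, 1+n-x). At 0/10 this is 0.8^11 = 0.086; at 0/9 it is 0.8^10 = 0.107. The other listed boundaries give 0.099 (1/17), 0.098 (2/24), 0.093 (3/31) and 0.099 (4/37), and one patient fewer gives more than 0.10 each time. Exact early-stopping probabilities with a maximum of 40 patients (inferred from the table) are 0.783, 0.240 and 0.045, against the stated 0.79, 0.24 and 0.044. The rule reproduces. The question is what it counts.

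**2. The definitions side by side.**

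| Category | Blood | Marrow | Outside blood and marrow |
|---|---|---|---|
| CR (8.1) | yes | yes | yes, but no scheduled imaging or CSF test |
| CRi (8.2) | yes | yes | not carried over |
| PR (8.3) | yes | yes | none |
| Progression (9.1) | blasts only | none | none |

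**3. Two eligible patients traced through the rules.**
- *Persisting mass, marrow blasts at or below 5%, low counts.* Not a CR, because the mass fails 8.1. The marrow result is as for CR and the counts are low, so 8.2 is met and the patient is a responder. No effect on the mass is needed. The low counts can come from the drug: Section 3.2.1 reports thrombocytopenia in 84.8% of lymphoma subjects, grade 3/4 in 59.5%. With no count minimum at entry, they can also predate treatment.
- *True partial shrinkage of a nodal mass, no marrow blasts.* Not a CR, because disease remains. Not a PR, because a marrow without blasts cannot show a 50% fall. Section 8.4 makes this a failure.

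A patient with both marrow and nodal disease whose counts recover and whose marrow blasts halve to 25% or less is a PR whatever the mass does.

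**4. How much of the endpoint runs through CRi.** Taking CRp as part of 8.2:
- Section 2.4: 7 of 12 responses, 58%.
- Section 2.5: 10 of 18, 56%.
- Section 2.6: (5 + 1) of 8, 75%.

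These shares show how much weight the category carries. They do not show that any of these responses was wrong.

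**5. Size.** One patient is 1/40 = 2.5 points in the weekly cohort and 1/49 = 2.0 points in the single-dose cohort. The documents give no count of affected patients. For illustration only, let a share f of patients lack marrow disease and a fraction q of their true non-responses be scored as CRi or PR. The apparent rate is p + f x q x (1 - p). With true p = 0.10 and a maximum of 40:

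| f | q | Apparent rate | Probability of stopping early |
|---|---|---|---|
| 0 | - | 0.10 | 0.78 |
| 10% | 25% | 0.10 + 0.10 x 0.25 x 0.90 = 0.123 | 0.65 |
| 10% | 50% | 0.10 + 0.10 x 0.50 x 0.90 = 0.145 | 0.51 |
| 20% | 50% | 0.10 + 0.20 x 0.50 x 0.90 = 0.19 | 0.28 |

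This covers only false responders. Missed nodal responses push the rate the other way. In the weekly rule (0/7, 1/10, 2/14, 3/17) one false responder turns 1/10, which stops, into 2/10, which continues.

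**The case against.** **CR already covers this.** A reader might infer that response is scored only on marrow and blood. That is wrong for CR: 8.1 excludes anyone with known residual disease, and the physical examination before each course can find clinical disease. This stands, and it narrows the point to CRi, PR and the missing scheduled test behind the radiologic clause. It can also be argued that CRi, by its name, is CR in everything but counts. That may be the intent, but the text of 8.2 carries over only blood and marrow results.

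**Progression.** A reader might infer that these patients can never meet progression and that this biases the response rate. Neither follows. Circulating blasts may appear later and satisfy 9.1. Other exits exist: "Investigator thinks a change of therapy would be in the best interest of the patient" (9.3), the CNS rule in 5.3, and "Patients with progression at any time or without objective response after 3 cycles will be taken off study" (5.2.4). Progression does not enter the primary endpoint or either stopping rule. What remains is that 9.1 misses marrow-only and extramedullary growth, while 5.2.4 relies on progression.

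**Marrow falls within the normal range.** On a literal reading, 4% to 2% blasts with normal counts is a PR. The reading is strained, because 8.3 speaks of recovery and 8.1 already calls such a marrow normal. The reported responses in Sections 2.4 to 2.6 contain no PRs. The point does not rest on it.

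**Isolated CNS relapse.** A reader might infer that intrathecal therapy could clear the disease and the drug be credited. The wording allows this, but nothing shows that such patients were intended or enrolled.

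**Effect on results so far.** The observed counts are far above the boundaries (18/32 against 3/31; 8/15 against 2/14). Even with all ten CRi/CRp responses in Section 2.5 recounted as failures, 8 of 32 would remain. The gap of 56% against 53% cannot be resolved anyway: the exact 95% intervals are 38-74% and 27-79%, and the weekly evaluation is descriptive. All this stands: no past decision is shown to be wrong.

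**Conclusion.** The point holds as a defect in the endpoint definition. An eligible patient with disease outside the marrow can be counted as a CRi responder with that disease still present, and a real nodal partial response with an uninvolved marrow must be counted as a failure. The radiologic clause of CR has no scheduled assessment behind it. This follows from the text and needs no assumption.

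The size and direction of the bias are unknown. The firm figures are 2.5 points per patient in 40 and 2.0 in 49. A reader might put the effect at 5 to 15 points, but that requires 2 to 6 of 40 patients to be affected and all to be misclassified in one direction, and the documents support neither. The stopping probabilities above likewise rest on assumed shares.

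**What to change.** 1. **Section 11.** Limit the primary response count and the stopping-rule denominators to patients with baseline marrow blasts above the 5% CR cut-off. Section 6.0 already requires a baseline marrow within 30 days, so this can be applied to patients already treated. The boundaries are responses over evaluable patients and can be used unchanged.
2. **Separate stratum.** Keep patients without marrow disease (lymphoma, other extramedullary, isolated CNS) eligible, but report them descriptively and apart, stating how disease was assessed at each site. Nodal criteria would not suit isolated CNS relapse.
3. **Sections 8.2 and 8.3.** State that the clinical/radiologic condition in 8.1 also applies to CRi, and that PR cannot be scored from marrow alone when extramedullary disease is present. Sections 6.0 and 7.0 should say which assessment supports that condition.
4. **Sections 4.1, 5.2.4 and 9.1.** Reconcile the circulating-blast definition of progression with the admission of lymphoma and extramedullary disease. No particular removal rule is proposed here.

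The cost is a few sentences and a slightly smaller primary denominator: if 2 to 6 of 40 patients were affected (an assumption), 38 to 34 would remain. No added accrual is needed for the definition change.
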